#### **5.4.2.1.3. NA Re-Treatment Criteria During FU**

The count and proportion of participants (and associated 90% CI) who meet the criteria for NA re-treatment at any time during FU will be summarized descriptively by intervention arm. In addition, the count and proportion of participants (and associated 90% CI) who met the criteria according to the flag on the CRF page of 'NA Re-treatment Criteria Assessment' during the follow-up phase will be summarized over time by intervention arm. The proportion of participants who met each sub-criteria will also be summarized by intervention arm.

The count and proportion of participants (and associated 90% CI) who actually re-started NA treatment during the follow-up phase on the basis of the 'Study Drug Administration for NA' CRF page will be summarized separately over time by intervention arm.

A cross-tabulation of participants who actually re-started NA treatment (re-started/not restarted) versus participants who met the above criteria (met/not met) will be presented over time by intervention arm.

#### **5.4.2.1.4. HBsAg Cut-offs**

The cut-offs for HBsAg values and decreases from baseline will be used in separate summaries over time by intervention arm. The count and proportion of participants who meet those HBsAg thresholds during the study will be summarized descriptively by intervention arm, and analysis phase over time and displayed in graphs like bar charts and/or radar plots.

Cross-tabulations overtime of quantitative HBsAg (<LLOQ, ≥LLOQ) versus qualitative HBsAg (positive, negative), respectively, will also be presented by intervention arm.

#### **5.4.2.1.5. HBsAg Seroclearance**

##### **5.4.2.1.5.1. On Treatment**

The count and proportion of participants (and associated 90% CI) who achieve HBsAg seroclearance over time during the study intervention phase will be summarized by intervention arm.

##### **5.4.2.1.5.2. Off Treatment**

The count and proportion of participants (and associated 90% CI) who achieve HBsAg seroclearance over time during FU will be summarized by intervention arm.

The count and proportion of participants who achieve HBsAg seroclearance will be evaluated by intervention arm at each of the following off-treatment time points: 12, 24, 36 and 48 weeks, respectively, after stopping all study interventions and without restarting NA treatment. In an additional summary, these proportions will be calculated with the denominator including only those participants who have reached the off-treatment timepoint (week 12, 24, 36 or 48), and have stopped all interventions including NA and have not restarted NA prior to the timepoint of interest.

For all time points, HBsAg seroclearance will be analyzed using the observed case data. LOCF will be used for selected time points (Section 5.4.2.1.1).

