3. OBJECTIVES AND ENDPOINTS

Below is the list of objectives and endpoints that will be evaluated in this study, delineating the details in alignment with the general objectives listed in the Master Protocol PLATFORMPAHPB2001. The details specific for this ISA are highlighted (colored fill).

Objectives	Endpoints
Primary	

 To evaluate the efficacy in terms of HBsAg changes from baseline for the treatment regimens of 24 weeks of JNJ-3989 + 24 weeks of NA + 12 or 24 weeks of PegIFN-α2a (with immediate or delayed start of PegIFN-α2a treatment), as compared to NA standard of care treatment. 	
 Proportion of participants with a reduction of at least 2 log₁₀ IU/mL in HBsAg levels from baseline at Week 24 (EOSI).
Secondary	

 To evaluate the safety and tolerability of the study intervention. 	
 Safety and tolerability including but not limited to the proportion of participants with (S)AEs and abnormalities in clinical laboratory tests (including hematology, blood biochemistry, blood coagulation, urinalysis, urine chemistry, renal biomarkers), 12-lead ECGs, vital signs, and ophthalmologic and physical examinations throughout the study.

 To evaluate the efficacy of the study intervention at the end of the 24-week treatment period. 	
 Proportion of participants meeting the protocol-defined NA treatment completion criteria based on the Week 24 (EOSI) or FU Week 2 results.

 To evaluate the efficacy of the study intervention during the FU period in those participants who met the protocol-defined NA treatment completion criteria based on the Week 24 or FU Week 2 results. 	
 Proportion of participants with HBsAg seroclearance at FU Week 24 and 48 (ie, 24 and 48 weeks after completion of all study interventions at Week 24) without re-starting NA treatment. Proportion of participants with HBV DNA <LLOQ at FU Week 24 and 48 (ie, 24 and 48 weeks after completion of all study interventions at Week 24) without re-starting NA treatment. Frequency of virologic and/or biochemical flares. Proportion of participants requiring NA re-treatment.

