### 1.1. Objectives and Endpoints

Objectives	Endpoints
Primary	

 
To evaluate the efficacy in terms of HBsAg changes from baseline for the treatment regimens of 24 weeks of JNJ-3989 + 24 weeks of NA + 12 or 24 weeks of PegIFN-<math>\alpha</math>2a (with immediate or delayed start of PegIFN-<math>\alpha</math>2a treatment), as compared to NA standard of care treatment.
 
	
 
Proportion of participants with a reduction of at least 2 log10 in HBsAg levels from baseline at Week 24 (EOSI).
 

Secondary	

 
To evaluate the safety and tolerability of the study intervention.
 
	
 
Safety and tolerability including but not limited to the proportion of participants with (S)AEs and abnormalities in clinical laboratory tests (including hematology, blood biochemistry, blood coagulation, urinalysis, urine chemistry, renal biomarkers), 12-lead ECGs, vital signs, and ophthalmologic and physical examinations throughout the study.
 

 
To evaluate the efficacy of the study intervention at the end of the 24-week treatment period.
 
	
 
Proportion of participants meeting the protocol-defined NA treatment completion criteria at Week 24 (EOSI) or FU Week 2 results.
 

 
To evaluate the efficacy of the study intervention during the FU period in those participants who meet the protocol-defined NA treatment completion criteria based on the Week 24 or FU Week 2 results.
 
	
 
Proportion of participants with HBsAg seroclearance at FU Week 24 and 48 (ie, 24 and 48 weeks after completion of all study interventions at Week 24) without re-starting NA treatment.
 

Objectives	Endpoints
	
 
Proportion of participants with HBV DNA <LLOQ at FU Week 24 and 48 (ie, 24 and 48 weeks after completion of all study interventions at Week 24) without re-starting NA treatment.
 
Frequency of virologic and/or biochemical flares.
 
Proportion of participants requiring NA re-treatment.
 

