##### **5.4.1.1.4.2. Off Treatment**

HBsAg seroclearance will be evaluated over time at each of the FU timepoints separately, with emphasis at FU Weeks 12, 24, 36 and 48 (i.e. 12, 24, 36, 48 weeks after completion of all study interventions at Week 24) and without restarting NA treatment.

For the analyses of seroclearance at the time points mentioned above, participants with HBsAg seroclearance at the respective time points (and without restarting NA treatment during the interval between the time of stopping the study intervention up to the analysis time point (FU Week 12, 24, 36 and 48)) will be considered as having achieved this endpoint.

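### The off-treatment HBsAg and HBV DNA endpoints have no planned summary explicitly in the population named by their objective, and the one restricted summary drops NA restarters from the denominator

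*SAP*

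**What the plan says.** Protocol Section 3 places one secondary follow-up objective "in those participants who met the protocol-defined NA treatment completion criteria based on the Week 24 or FU Week 2 results", and SAP Section 1.1 repeats that population. Two of its endpoints are "Proportion of participants with HBsAg seroclearance at FU Week 24 and 48" and "Proportion of participants with HBV DNA <LLOQ at FU Week 24 and 48", each qualified as without re-starting NA.

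SAP 5.4.1.1.4.2 applies the qualifier: a participant achieves the endpoint only with seroclearance at the time point and "without restarting NA treatment during the interval between the time of stopping the study intervention up to the analysis time point". SAP 5.4.1.1.10 puts the same condition on suppressed HBV DNA.

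For the analysis, SAP 5.4.2.1.5.2 (seroclearance) and 5.4.2.1.10 (HBV DNA) each plan two off-treatment summaries:

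- The first reads, for seroclearance, "The count and proportion of participants who achieve HBsAg seroclearance will be evaluated by intervention arm at each of the following off-treatment time points". No denominator is given. SAP Section 4 makes the FAS the primary efficacy set, and 5.4.2 calls for observed cases.
- The second, described as additional, has a denominator of those who reached the time point and "have stopped all interventions including NA and have not restarted NA prior to the timepoint of interest".

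SAP 5.4.2.1.14 does plan an analysis of off-treatment flares in those who met the completion criteria and stopped NA. SAP Appendix 2 declares no change from the protocol's analyses.

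**The concern.** The objective asks how many of the participants who met the completion criteria hold a response without NA. The natural estimate is responders divided by everyone who met the criteria, with restarters kept in the denominator as non-responders. I will call these participants completers.

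The first planned summary, read with the FAS default, also includes participants who never qualified to stop NA. It mixes the chance of qualifying with the durability of response afterwards. The second conditions on something that happens after NA is stopped, and it removes participants whom the endpoint definition counts as non-responders.

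For HBV DNA that removal is partly driven by the outcome. Three of the five re-treatment criteria in Protocol 6.5.2 involve HBV DNA: above 1,000,000 IU/mL; confirmed above 2,000 IU/mL with ALT above 5x ULN; and confirmed above 20,000 IU/mL. None is an HBsAg level, although HBsAg dynamics are among the things to weigh in the decision to restart. For seroclearance the dependence is therefore indirect.

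What is at stake is the comparison of regimens. SAP 5.4.2 allows comparisons of secondary endpoints between arms without multiplicity adjustment, and the restricted rate can differ between arms only because restart rates differ.

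**Working it through.** **Inputs from the documents.** Arm size is 34 (SAP Section 3). As a check, 30/(1 - 0.10) = 33.3, which rounds up to 34, and 3 x 34 = 102, as stated. Intervals are two-sided 90% Clopper-Pearson (SAP 5.1.5, 5.1.7). The documents give no expected completer, restart or off-treatment response rate, so the plan has no figure of its own to reproduce here. The counts below are assumptions.

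**Formulas.** Let N be the arm size, c the number of completers, r the number of completers who restart NA, and s the number of responders. Take complete data, and let those who stop NA be the completers.

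- Whole arm: s/N
- Objective's population: s/c
- Non-restarters: s/(c - r)

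The third divided by the second is c/(c - r) = 1/(1 - r/c). This depends only on the restart fraction:

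| Restart fraction r/c | 10% | 20% | 30% | 40% | 50% |
|---|---|---|---|---|---|
| Inflation factor | 1.11 | 1.25 | 1.43 | 1.67 | 2.00 |

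**Illustrations over a range, N = 34:**

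| c | r | s | s/N | s/c (90% CI) | s/(c - r) (90% CI) |
|---|---|---|---|---|---|
| 10 | 2 | 2 | 5.9% | 20.0% (3.7 to 50.7) | 25.0% (4.6 to 60.0) |
| 10 | 4 | 2 | 5.9% | 20.0% (3.7 to 50.7) | 33.3% (6.3 to 72.9) |
| 17 | 3 | 3 | 8.8% | 17.6% (5.0 to 39.6) | 21.4% (6.1 to 46.6) |
| 17 | 7 | 3 | 8.8% | 17.6% (5.0 to 39.6) | 30.0% (8.7 to 60.7) |
| 24 | 5 | 5 | 14.7% | 20.8% (8.6 to 38.9) | 26.3% (11.0 to 47.6) |
| 24 | 10 | 5 | 14.7% | 20.8% (8.6 to 38.9) | 35.7% (15.3 to 61.0) |

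**Between arms.** Take two arms of 34, each with 20 completers and 4 responders. Both have 4/34 = 11.8% over the arm and 4/20 = 20.0% over completers. If 2 restart in one arm, its non-restarter rate is 4/18 = 22.2% (8.0 to 43.9). If 10 restart in the other, it is 4/10 = 40.0% (15.0 to 69.6). The arm with more restarts looks better, although the completer rates are equal. This holds responders fixed, so the extra restarters come from participants who would not have responded anyway.

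**Does another analysis supply the completer rate?** Functional cure (SAP 5.4.2.1.5.3) is summarised by arm. The NA reference timepoint (5.1.6) sets a reference value, not a denominator. Time to HBV DNA <LLOQ (5.4.1.3.3) covers only completers who were re-treated. The flare analysis (5.4.2.1.14) uses nearly the right population, but for flares only.

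**The case against.** The strongest reply is that the plan does not hide restarts. They already count as non-achievement in the first summary, through the endpoint definition, and leave the denominator only in a summary labelled as additional. SAP 5.4.2.1.2 reports how many met the completion criteria at Week 24, and 5.4.2.1.3 reports actual restarts over time, both by arm. A reader could approximate the completer rate from these. Functional cure already has a missing-as-non-response sensitivity analysis. These are secondary phase 2 summaries without multiplicity control. All of this stands, and it limits the weight of the point. It does not provide the estimate that the objective names, or its interval.

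Three stronger readings are tempting, and the documents do not support them.

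- A reader might say that the plan analyses everyone. The first denominator is not stated. The FAS follows only from the default in Section 4, and SAP 5.4 takes the endpoints from Section 1.1, where the completer population is named.
- A reader might call the restricted rate conditional on not having failed. It is conditional on not having restarted NA. The LLOQ is 20 IU/mL (SAP Table 5), while the re-treatment criteria based on HBV DNA start above 2,000 IU/mL. Participants between these levels can stay off NA and remain in the denominator as failures.
- A reader might say that the restricted rate always rises with more restarts. It does so only if the number of responders is unchanged.

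**Conclusion.** The point holds as a mismatch between an objective and its planned analysis. For HBsAg seroclearance and HBV DNA <LLOQ, no summary is explicitly set in participants who met the completion criteria, with restarters kept as non-responders. The additional summary overstates the rate in that population by 1/(1 - restart fraction), which is 1.25 times at 20% and 1.67 times at 40%. The formula is exact under complete data when those who stop NA are those who met the criteria; the restart fractions are assumptions.

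The two groups need not coincide. Stopping NA on FU Week 2 results is discretionary, and Protocol 6.5.1 lets completion be considered after an ALT elevation judged unrelated to HBV activity. Requiring participants to have reached the time point also removes early withdrawals.

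A reader might infer that the plan inflates its off-treatment result overall. The documents do not support that: the first summary keeps restarters as non-achievers, and the restricted one is marked as additional. The change is worth making because the restricted rate can separate arms whose completer rates are equal, and the correction is cheap.

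**What to change.** In SAP 5.4.2.1.5.2 and 5.4.2.1.10:

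1. State the denominator of the first summary (FAS by arm).
2. Add, at FU Weeks 24 and 48, a by-arm proportion with 90% CI over all participants who met the NA completion criteria on Week 24 or FU Week 2 results. Count NA restart before the time point as non-response.
3. Show beside it the number who met the criteria but did not stop NA. The objective's population is defined by meeting the criteria, so these participants belong in the denominator and should be visible.
4. Keep the non-restarter summary as a labelled descriptive supplement, with the number of restarters per arm.
5. If wanted, add a missing-as-non-response version as a sensitivity analysis, as already planned for functional cure. The main version can stay on observed cases.

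The cost is SAP wording, a population flag and one extra table row per endpoint. Reported rates among participants who completed NA will be lower than the non-restarter rates.

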##### **5.4.2.1.5.3. Functional Cure**

The count and proportion of participants (and associated 90% CI) who achieve FC at each of the selected FU time points will be summarized descriptively by intervention arm.

The main analysis will be on observed cases data with no imputation of missing values.

Two sensitivity analyses will be performed.

1. Missing as non-response: If participants withdrew from the study prior to the selected FU time point or had missing HBsAg values at the selected FU time point, they will be considered as non-responders.
2. LOCF: If participants withdrew from the study prior to the selected FU time point, they will be considered as non-responders. The LOCF rules to handle missing data will be applied to selected time points as explained in Section 5.4.2.1.1.

##### **5.4.2.1.6. Treatment Failure**

The count and proportion of on-treatment failure participants (and associated 90% CI) will be summarized by intervention arm.

##### **5.4.2.1.7. HBsAg Seroconversion**

The count and proportion of participants (and associated 90% CI) who achieve HBsAg seroconversion will be summarized descriptively by intervention arm and analysis phase.

For participants achieving HBsAg seroconversion, descriptive statistics will be calculated for the level of anti-HBs antibodies at the timepoint when achieving the HBsAg seroconversion. In an additional summary, the level of anti-HBs antibodies at the specific timepoint will be summarized for the subset of the participants achieving HBsAg seroconversion at any time before or at that given timepoint.

In addition, the count and proportion of participants (and associated 90% CI) with appearance of anti-HBs antibodies but without seroclearance of HBsAg will also be summarized by intervention arm and analysis phase.

#### **5.4.2.1.8. HBeAg Cut-offs**

The cut-offs for HBeAg values will be used in separate summaries over time by intervention arm. The count and proportion of participants who meet those HBeAg thresholds during the study will be summarized descriptively by intervention arm and analysis phase over time and displayed in graphs like bar charts and/or radar plots.

Cross-tabulations overtime of quantitative HBeAg (<LLOQ, ≥LLOQ) versus qualitative HBeAg (positive, negative), respectively, will also be presented by intervention arm.

#### **5.4.2.1.9. HBV DNA Cut-offs**

The cut-offs for HBV DNA values will be used in separate summaries over time by intervention arm. The count and proportion of participants who meet those HBV DNA thresholds during the study will be summarized descriptively by intervention arm and analysis phase over time.

#### **5.4.2.1.10. Suppressed HBV DNA**

The count and proportion of participants (and associated 90% CI) with HBV DNA <LLOQ (overall and separately for HBV DNA detectable and HBV DNA TND) will be evaluated by intervention arm and analysis phase over time.

The count and proportion of participants (and associated 90% CI) with HBV DNA <LLOQ (overall and separately for HBV DNA detectable and HBV DNA TND) will be evaluated by intervention arm at each of the FU Weeks 12, 24, 36, and 48, respectively, after stopping all study interventions at Week 24 and without restarting NA treatment.

In an additional summary, these proportions will be calculated with the denominator including only those participants who have reached the off-treatment timepoint (week 12, 24, 36 or 48), and have stopped all interventions including NA and have not restarted NA prior to the timepoint of interest.

The count and proportion of participants (and associated 90% CI) with HBV DNA <LLOQ (overall and separately for HBV DNA detectable and HBV DNA TND) after restart of NA treatment during follow-up will also be presented by intervention arm.

The number of occurrences each subject has HBV DNA <LLOQ (overall and separately for HBV DNA detectable and HBV DNA TND) will be determined and summarized by intervention arm

using frequency distributions and descriptive statistics. Additionally, the number of occurrences will be displayed graphically.

For all time points, HBV DNA <LLOQ will be analyzed using the observed case data. LOCF will be used for selected time points (Section 5.4.2.1.1).

The same analyses will also be performed for HBV DNA < 60 IU/mL.

#### **5.4.2.1.11. ALT Normalization**

The count and proportion of participants (and associated 90% CI) who achieve ALT normalization on treatment and off treatment but without restarting NA treatment will be summarized descriptively over time by intervention arm, only for the subjects who had ALT elevation ( $ALT \geq ULN$ ) at baseline.

The count and proportion of participants (and associated 90% CI) who have  $ALT \geq ULN$  before NA re-treatment and reach ALT normalization after NA re-treatment during follow-up will be summarized by intervention arm.

#### **5.4.2.1.12. Partial Cure**

The count and proportion of participants (and associated 90% CI) who achieve partial cure during the study will be summarized descriptively by intervention arm at the selected FU time points.

The main analysis will be on observed cases data with no imputation of missing values.

Two sensitivity analyses will be performed.

1. Missing as non-response: If participants withdrew from the study prior to the selected FU time point or had missing HBsAg or HBV DNA values at the selected FU time point, they will be considered as non-responders.
2. LOCF: If participants withdrew from the study prior to the selected FU time point, they will be considered as non-responders. The LOCF rules to handle missing data for HBsAg and HBV DNA will be applied to selected time points as explained in Section 5.4.2.1.1.

#### **5.4.2.1.13. Virologic Breakthrough**

The count and proportion of participants (and associated 90% CI) who experience a virologic breakthrough and those who experience virologic breakthrough followed by on-treatment biochemical flare will be summarized, respectively, by intervention arm and analysis phase.

#### **5.4.2.1.14. Flares**

The incidence rate will be calculated and summarized for each type of on-treatment or off-treatment flares (virologic, biochemical and clinical) separately, as well as the overall incidence of participants experiencing at least one flare, regardless of type, by intervention arm. Additionally, for each participant the total number of flares the participant experienced will be counted by type.

Such counts will be used to summarize the distribution of the total number of flares by type and intervention arm.

For on-treatment biochemical flares, the incidence of flares causing treatment discontinuation will be summarized by intervention arm. Further, for off-treatment flares, the count and percentage of participants who experienced a flare followed by NA re-treatment will be summarized by flare type and intervention arm. Similarly, the incidence of flares followed by the achievement of HBsAg seroclearance (at any time) will be summarized by flare type and intervention arm.

Additional analysis for off-treatment flares will be performed for those who met the NA treatment completion criteria and stopped NA.

Flares that are associated with signs of liver decompensation will be provided in a listing.

#### **5.4.2.2. Continuous Endpoints**

##### **5.4.2.2.1. HBsAg, HBeAg, HBV DNA and ALT**

Descriptive statistics on actual values (original unit and  $\log_{10}$  transformed values) and changes from baseline ( $\log_{10}$  transformed values) over time in HBsAg, HBeAg, HBV DNA, and ALT (original unit) will be summarized by intervention arm. Mean (+/- SE) plots of the actual values, change from baseline ( $\log_{10}$  transformed) and change from RTs will be presented over time per endpoint by intervention arm and analysis phase. The change from baseline value to the nadirs (i.e. maximum decrease for each participant) in HBsAg, HBeAg and HBV DNA will be summarized descriptively by intervention arm. Box plots of the changes to nadirs in HBsAg and HBV DNA will display the distribution by intervention arm.

Change from baseline based on  $\log_{10}$  transform for quantitative HBsAg, HBeAg and HBV DNA will be analyzed using mixed effects model for repeated measures [MMRM]) including intervention arm, analysis time point (week), their interaction, and 2 randomization stratification factors (ie, country grouping as proxy for HBV genotype (GT) at enrollment [Poland (predominantly GT-A) vs Russia (predominantly GT-D) vs all other countries (other or mixed GT prevalence)] and absolute HBsAg value at baseline [ $<1,000$  IU/mL versus  $\geq 1,000$  IU/mL]) and baseline blood marker categorical variable as fixed effects. In addition, the above model will be augmented with an intervention arm-by-analysis week interaction term (i.e. treatment-by-time interaction term) to evaluate the change of treatment effect over time and the intervention arm-by-baseline interaction term. The covariance structure will include a random intercept at the level of the participant to capture between-participant variability, while within-participant variability will be captured with an unstructured (type=UN) covariance matrix. In case of convergence problems, simpler variance-covariance structures such as Toeplitz or AR (1) will be considered. The selection of any of these structures will be determined after exploration of the observed correlation structure. The LS mean of change from baseline, standard error (SE), 90% confidence interval (CI) and p-values will be provided.

Descriptive statistics on actual values (original unit and  $\log_{10}$  transformed values) and changes from baseline ( $\log_{10}$  transformed values) at end of treatment in HBsAg, HBeAg and HBV DNA

will be summarized by study intervention arm by outcome response (i.e. by reduction of at least 2 log10 IU/mL in HBsAg levels from baseline at Week 24, by HBsAg seroclearance at Week 24, FU Week 24 and FU Week 48, and by partial cure status at Week 24, and for participants who achieved functional cure at FU Week 24 and FU Week 48).

Spaghetti plots for both absolute values and changes from baseline of HBsAg and HBV DNA will be presented over time per blood marker by intervention arm and by selected subgroups (Section 5.7.7.1).

Waterfall plots for changes from baseline and RTs of HBsAg, HBeAg, and HBV DNA will also be presented.

Descriptive statistics of the absolute values, changes from baseline and RTs over time in ALT will be summarized by intervention arm and analysis phase for those participants who had ALT elevation at baseline. An additional summary of descriptive statistics of the ALT absolute values and changes from baseline over time will be summarized by intervention arm and analysis phase for those participants who had ALT values within the normal range at baseline.

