- d. Visits at follow up Week 8, 16, 20, 28, 32, 40, and 44 are optional for participants who continue NA treatment or have restarted NA treatment during the follow up period (provided that their HBV DNA and ALT values are stable) and mandatory for participants who do not continue NA treatment during the follow up period. Participants who experience

ALT/AST elevations as defined in Section 8.3.6.2, Intervention emergent ALT/AST Elevations, will be monitored on a weekly basis or more frequently until ALT and AST levels have returned to <5x ULN and HBV DNA is <20,000 IU/mL.

- e. If necessary (eg, for operational reasons), the Screening Period may be extended up to a maximum of 8 weeks in agreement with the Sponsor.
- f. Only applicable for participants of Arms 1 and 3.
- g. Only applicable for participants of Arm 2.
- h. Both the Platform Master ICF and the ISA ICF must be signed before the first study related activity.
- i. Minimum criteria for the availability of documentation supporting the eligibility criteria are described in the source documents section in Attachment 3 of the Master Protocol PLATFORMPAHPB2001. Clinical status will be checked and documented at screening and again before first dose of study intervention. If a participant's clinical status changes (including any available laboratory results or receipt of additional medical records) after screening but before the first dose of study intervention is given such that he or she no longer meets all eligibility criteria, then the participant should be excluded from participation in the study.
- j. Only applicable for Arm 2: Exclusion criterion A24 regarding contraindications to the use of PegIFN α 2a needs to be checked and documented again prior to the first dose of PegIFN α 2a on Week 12. If an Arm 2 participant's clinical status changes (including any available laboratory results or receipt of additional medical records) after randomization but before the first dose of PegIFN α 2a is administered, such that he or she meets exclusion criterion A24, then the participant will continue treatment as planned but without PegIFN α 2a (ie, JNJ 3989+NA until Week 24).

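### The MMRM in SAP 5.4.2.2.1 is not identified as specified: the random intercept is redundant with the unstructured matrix, and Weeks 2 and 14 are never scheduled in the same participant

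*SAP*

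**What the plan says.** SAP 5.4.2.2.1 plans a mixed model for repeated measures on log10 change from baseline in HBsAg, HBeAg and HBV DNA. It promises least-squares means, standard errors, 90% intervals and p-values.

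- **Fixed effects:** "including intervention arm, analysis time point (week), their interaction, and 2 randomization stratification factors", plus "baseline blood marker categorical variable as fixed effects". The section does not define the baseline categories. A later sentence adds the arm-by-week interaction again, together with arm-by-baseline.
- **Covariance:** "The covariance structure will include a random intercept at the level of the participant to capture between-participant variability". On top of this intercept, the same sentence states that "within-participant variability will be captured with an unstructured (type=UN) covariance matrix".
- **Fallback:** "In case of convergence problems, simpler variance-covariance structures such as Toeplitz or AR (1) will be considered". On how to choose among the alternatives, the SAP adds: "The selection of any of these structures will be determined after exploration of the observed correlation structure".
- **Visits:** the Schedule of Activities (Protocol 1.3) marks Week 2 "Only applicable for participants of Arms 1 and 3" (footnote f) and Week 14 "Only applicable for participants of Arm 2" (footnote g). SAP Table 4 (section 5.1.3) lists both as analysis time points, and the MMRM text excludes neither. Section 5.1.3 also includes the end-of-treatment (EOT) record in analyses over time by default. Table 4 defines that record as the last post-baseline visit of the treatment period.

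**The concern.** A participant random intercept adds the same constant to every variance and covariance. An unstructured matrix can reproduce that shift itself, so the data cannot separate the two. The covariance between Week 2 and Week 14 has no scheduled joint observations, and an arm-by-week term has no data where a week is not scheduled in an arm.

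Change in HBsAg over time is a listed secondary endpoint (Protocol 3, SAP 1.1), and this model is the planned source of inference for it. At stake is whether the fit is determined by the SAP or by what the software does with an over-parameterised model, followed by a covariance choice made after seeing the data in an open-label study whose sponsor runs the interim analyses. A smaller cost is the precision lost by categorising a measured baseline.

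**Working it through.** The documents give no figure for this model, so there is none to reproduce.

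**1. Covariance parameters against what the schedule can show.** An unstructured matrix on T visits has T(T+1)/2 parameters. Identifiability is the rank of the map from those parameters to the variances and covariances of jointly scheduled visits.

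| Visits and structure | Parameters | Rank |
|---|---|---|
| 8 treatment weeks (2, 4, 8, 12, 14, 16, 20, 24), unstructured | 8×9/2 = 36 | 35 |
| Same, plus random intercept | 37 | 35 |
| Same, Toeplitz | 8 | 8 |
| Same, Toeplitz plus random intercept | 9 | 8 |
| 6 common weeks (4, 8, 12, 16, 20, 24), unstructured | 6×7/2 = 21 | 21 |
| Same, plus random intercept | 22 | 21 |

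AR(1) plus a random intercept is identified (3 of 3, checked on six visits). In the 36-parameter case the one missing dimension is the Week 2/Week 14 covariance.

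**2. Likelihood check.** Data were simulated for 68 participants on the Arm 1/3 schedule and 34 on the Arm 2 schedule. The log-likelihood was −171.955 at intercept variances of 0, 0.05, 0.10 and 0.15, with the unstructured part adjusted to match. It was the same at three values of the Week 2/Week 14 covariance. Both directions are flat, while the covariance among visits scheduled together does not change.

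**3. Arm-by-week cells.** There are 3×8 = 24 cells. Arms 1 and 3 have 7 scheduled weeks each and Arm 2 has 7, so 14 + 7 = 21 are filled. The empty ones are Arm 2/Week 2, Arm 1/Week 14 and Arm 3/Week 14. Each arm lacks one week, so with arm-by-week in the model a least-squares mean averaged over all eight weeks is not estimable for any arm.

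**4. Visit spacing under the fallback.** Gaps between the eight weeks are 2, 4, 4, 2, 2, 4 and 4. Toeplitz and AR(1), as usually coded, treat them as equal. The six common weeks are all 4 weeks apart.

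**5. Baseline.** Assume the categories are the HBsAg subgroups of SAP Table 8 (section 5.7.7.1: cuts at 100, 1,000 and 10,000 IU/mL) and that log10 HBsAg is normal with mean 2.5–3.5 and SD 0.6–1.0. Four categories then keep about 80–88% of the R² of the continuous value. At an assumed baseline correlation r = 0.5:

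- continuous: 1 − 0.25 = 0.75
- 80% kept: 1 − 0.80×0.25 = 0.80, and 0.80/0.75 = 1.07
- 88% kept: 1 − 0.88×0.25 = 0.78, and 0.78/0.75 = 1.04

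Residual variance is thus about 4–7% higher. With these cuts the stratification factor at 1,000 IU/mL is an exact combination of the categories (intercept, stratum and three category indicators: 5 columns, rank 4).

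**6. HBeAg.** Inclusion criterion A03 requires HBeAg-negativity, and SAP Table 5 (section 5.1.9) imputes values below 0.11 IU/mL as 0.055. Where both values are below the limit, the change is exactly zero.

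**The case against.** The strongest reply is that the two flat directions are nuisance parameters. That stands. Software may set the intercept variance to zero or print a Hessian warning and still return valid results for Week 24 and every other scheduled cell. A reader might infer that the model cannot be fitted; the documents do not support that. The empty cells come from the design, and no model could compare arms at a visit that one of them does not have.

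It is also fair that the fallback may never be used, since it is tied to convergence problems. A reader might infer that the analysis must end on a misspecified, data-chosen covariance with unreliable intervals. That is a prediction: the list of alternatives is open-ended, and the documents give no figures showing that the spread of HBsAg change grows with time. What remains is that no order is fixed, the choice follows inspection of the data, and Toeplitz with the intercept retained is still unidentified.

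Two larger magnitudes are tempting but unsupported:

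- 21×22/2 = 231 covariance parameters would need one model across treatment and follow-up. The SAP does not say this; sections 5.1.3 and 5.4.2 allocate visits and organise summaries by phase.
- A 12% rise in residual variance (1 − 0.637×0.25 = 0.841; 0.841/0.75 = 1.12) assumes a median split. The SAP's HBsAg groupings have four levels (Table 8) or five (Table 12), and the two-level factor at 1,000 IU/mL is already a separate term.

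That HBeAg changes will mostly be zero is an inference from the entry criterion and the imputation rule, not a reported figure. Only HBsAg is a listed change-from-baseline endpoint among the three markers.

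Finally, the primary endpoint uses an exact binomial test, and secondary comparisons carry no multiplicity control, so the reach of the defect is limited.

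**Conclusion.** The point holds as a specification defect. Over the eight treatment weeks the covariance model is over-parameterised by two (37 parameters, rank 35), and three of 24 arm-by-week cells are empty. This follows from the algebra and the schedule and needs no assumption about the data. The one qualification is that an off-window or unscheduled sample could fall in the Week 2 or Week 14 analysis window (days 2–22 and 93–106), too rarely to support an estimate.

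The practical consequence is moderate. Results at scheduled visits survive, averages over all treatment weeks do not, and the covariance finally used is not fixed in advance. The baseline loss of about 4–7% in residual variance is modest and rests on the Table 8 cuts, the assumed HBsAg distribution and r = 0.5. It matters mainly for HBsAg, because entry criteria leave little baseline variation in HBeAg and HBV DNA. The primary analysis is not affected.

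**What to change.** Amend SAP 5.4.2.2.1:

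1. Drop the participant random intercept.
2. Fit the unstructured matrix on the treatment weeks scheduled in all arms (4, 8, 12, 16, 20, 24). State that the EOT record is excluded, because it repeats the last treatment visit and would make the matrix singular.
3. Enter continuous log10 baseline HBsAg in place of the categorical variable, keep the two stratification factors, and list arm-by-week once.
4. Prespecify the fallback order and its trigger, with no random intercept under Toeplitz. For example: Toeplitz, then AR(1). On the six common weeks, equal spacing is correct for both.
5. Summarise HBeAg change descriptively and leave it out of the MMRM.

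Further choices, such as the degrees-of-freedom method or robust standard errors, are preferences and are not needed to cure the defect.

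The cost is SAP wording, with no new data, visits or participants. The downside is that Weeks 2 and 14 are reported descriptively only.
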